#### **13.4.8.2.3. Overall Outcome**

A summary with the number and percentage of subjects with clinical cure and mycological eradication (overall outcome) at the TOC visit will be performed by Candida Species of the baseline yeast and overall. The subjects who cannot determine the overall outcome at the TOC visit will be removed from the analysis and no missing data will be imputed for both clinical outcome and mycological outcome.

Overall outcomes will be assessed at the TOC Visit (Day 11) according to the following definitions:

- Overall Success: A subject with the achievement of both a clinical cure and mycological eradication;
- Overall Failure: A subject with either not clinical cure or mycological persistence.

The analyses for overall outcome will only be conducted for the mITT set. The overall outcomes will be listed with baseline species referenced aside in a listing.

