21.3.14.3 Handling of Missing Data and Early Withdrawals

For the efficacy analyses, subjects who do not have a TOC (Day 11) assessment will be assigned as treatment failures. For subjects who withdraw from the study early, every effort will be made to collect TOC (Day 11) visit information at the point of withdrawal.

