#### **13.4.4.1. Sample Size**

The primary endpoint of the study is the percentage of subjects with Clinical Success (at least 50% reduction from Baseline in the total composite VSS score with no additional antifungal therapy required based on investigator's judgment) at the TOC visit. As this is a single arm sub-study, a statement regarding the Clinical Success rate and 95% confidence interval will be produced. It is estimated that 60 subjects will be included based upon published fluconazole failure rates. With a study of this size, if the Clinical Success rate for ibrexafungerp were 50%, this would correspond to a 95% confidence interval spanning from 36.8% to 63.2%. Given it is expected that the Clinical Success for ibrexafungerp in subjects who have already failed fluconazole will be low as these subjects had already failed to respond, a sub-study of this size is appropriate to assess the efficacy of ibrexafungerp in this patient population.

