#### **13.4.4.4. Handling of missing data**

For categorical response endpoints including clinical outcome, mycological outcome, symptom outcome, and clinical improvement, subjects will be considered a non-responder for the non-responder imputation (NRI) analysis if they are missing categorical response data at the specific visit. Randomized subjects without at least 1 post-baseline observation will also be defined as non-responder for the NRI analysis such that subjects who have a missing value at the TOC visit or FU visit will be assigned as treatment failures, i.e., non-responders or positive mycological outcome for the corresponding visit. Randomized subjects without study treatment will be excluded from all analysis.

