#### **13.4.8.1.1. Primary Analysis**

The primary efficacy analysis will be performed on the mITT set at the TOC visit. The number and percentage of subjects with clinical success at the TOC visit will be presented. The 95% confidence interval of the clinical success rate will be calculated using the method of Clopper and Pearson. Missing data for clinical outcome will be imputed using the NRI method described in Section 13.4.4.4. Additional summarizations will be performed by Candida Species of the baseline yeast, but not subject to formal statistical analysis.

The same analysis employing the same methods as for the primary analysis will be performed for the ITT set to assess clinical success at TOC visit. Missing data for clinical outcome will be imputed using the NRI method described in Section 13.4.4.4.

A sensitivity analysis using the mITT set will be performed where subjects with the imputed clinical outcome using the NRI method at TOC visit will be removed from the analysis.

Summary of the number and percentage of subjects with continued clinical success at the Follow-up (FUP) visit, which defined as continued clinical success in subjects who achieved Clinical Success at the TOC visit, will be provided based on the ITT, and mITT sets.

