#### **13.4.11. Changes in the Planned Analysis**

For the clinical failure definition, the texts “less than 50% reduction from baseline in the total composite VSS score” was used to replace “persistence and/or worsening of signs and symptoms” we have in the protocol.

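### The sub-study's Overall Outcome leaves out undeterminable subjects where the protocol counts a missing TOC as failure, so the composite can exceed its own Clinical Cure component

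*SAP*

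**What the plan says.** The proportion with both Clinical Cure and Mycological Eradication at TOC is a named secondary efficacy endpoint of the sub-study (Protocol 21.3.5.2; SAP 13.4.3.2.2). SAP 13.4.8.2.3 calls it the Overall Outcome and analyses it in the mITT set only. Subjects whose overall outcome cannot be determined at TOC "will be removed from the analysis and no missing data will be imputed for both clinical outcome and mycological outcome". The same section makes failure on either component an Overall Failure. It plans no version with imputation.

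The surrounding rules differ:

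- Protocol 21.3.14.3, on the sub-study efficacy analyses: "subjects who do not have a TOC (Day 11) assessment will be assigned as treatment failures".
- SAP 13.4.4.4 sets non-responder imputation (NRI) "For categorical response endpoints including clinical outcome, mycological outcome, symptom outcome, and clinical improvement", with the consequence that "subjects who have a missing value at the TOC visit or FU visit will be assigned as treatment failures".
- SAP 13.4.8.2.2 repeats this for culture: missing TOC data become mycological persistence.
- SAP 13.4.8.1.1 uses NRI for the primary endpoint and removes imputed subjects only in a sensitivity analysis.
- SAP 13.4.11 lists a single change from the protocol, which opens "For the clinical failure definition". It does not mention missing data.

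**The concern.** A subject must succeed on both components to be an Overall Success, so the composite rate should never be above either component rate. That ordering is guaranteed only if all three rates share a denominator. Here the components are divided by the full mITT, with missing counted as failure, while the composite is divided by a smaller number. The tables could then show more subjects, in percentage terms, both cured and eradicated than cured. A reader would have no explanation, because the departure from the protocol is neither declared nor justified. The sub-study has no control arm, so the level of the rate is the result itself.

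**Working it through.** **The plan's own figure.** The only numerical target for the sub-study is the interval for a 50% Clinical Success rate in 60 subjects, 36.8% to 63.2% (SAP 13.4.4.1). The exact Clopper-Pearson interval for 30/60 reproduces it. No figure is given for the Overall Outcome.

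**Who is removed.** Only subjects whose overall outcome is undeterminable. A subject with one known failed component stays in as an Overall Failure. So does an early terminator who took additional antifungal therapy, who fails both components under SAP 13.4.8.2.1 and 13.4.8.2.2. The removed group is therefore mainly subjects with no TOC data and no additional therapy.

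**Notation.** N = mITT size; m = subjects removed; C = clinical cures; S = overall successes, with S ≤ C.

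- Clinical Cure under NRI: C/N. SAP 13.4.8.2.1 has no missing-data sentence of its own, but Clinical Cure is a clinical outcome, so SAP 13.4.4.4 covers it.
- Overall Success as the SAP has it: S/(N − m).
- Overall Success under the protocol rule: S/N.

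**Two results.** First, S/(N − m) > S/N whenever m ≥ 1 and S ≥ 1; the ratio of the two is N/(N − m). Second, S/(N − m) > C/N exactly when S/C > (N − m)/N. The same algebra applies to eradication. Under the protocol rule, S/N can never exceed C/N.

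**Numbers.** The documents give neither mITT size nor dropout rate. N = 60 (the planned sub-study size) and m = 3 to 12 (5% to 20%) are assumptions, with about half of the determinable subjects cured.

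| m | C | S | Overall, SAP: S/(N − m) | Clinical Cure: C/N | Overall, protocol rule: S/N | Inversion needs S/C above |
|---|---|---|---|---|---|---|
| 3 | 28 | 28 | 28/57 = 49.1% | 46.7% | 46.7% | 95% |
| 6 | 27 | 27 | 27/54 = 50.0% | 45.0% | 45.0% | 90% |
| 6 | 27 | 26 | 26/54 = 48.1% | 45.0% | 43.3% | 90% |
| 6 | 27 | 24 | 24/54 = 44.4% | 45.0% | 40.0% | 90% |
| 9 | 26 | 26 | 26/51 = 51.0% | 43.3% | 43.3% | 85% |
| 12 | 24 | 24 | 24/48 = 50.0% | 40.0% | 40.0% | 80% |

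The mITT requires a positive Baseline culture, so it may be smaller than 60. With an assumed N = 48 and 20 cures, Clinical Cure is 20/48 = 41.7%. If all 20 are eradicated, the composite is 20/44 = 45.5% with 4 removed and 20/40 = 50.0% with 8 removed. With fewer eradicated there need be no inversion: 18/44 = 40.9% and 16/40 = 40.0%.

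**How close S is likely to be to C.** Protocol 21.3.6.1 calls for a TOC culture only when signs and symptoms have not improved or have worsened. SAP 13.4.8.2.2 counts a symptom-free subject without a specimen as eradicated. A cured subject will therefore usually be eradicated by rule, which puts S near C, where inversion occurs.

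**The case against.** Several points on the other side have force.

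- *The removed group is narrow.* A reader might infer that everyone with missing TOC data is dropped. The SAP does not say that, for the reasons given in the working. In addition, Protocol 21.3.7.3 asks that subjects withdrawing by TOC have the TOC procedures at early termination, which should keep m small. This stands.
- *The protocol may intend imputation for the primary only.* Protocol 21.3.14.5.2 imputes failure for the primary endpoint and says that other efficacy data are only summarised. But a lack of formal testing is not an exemption from 21.3.14.3, which speaks of the efficacy analyses without exception.
- *The SAP need not contradict itself.* SAP 13.4.4.4 does not name the overall outcome, and a specific rule can override a general one. This stands in part. What remains is an undeclared departure from the protocol, and an analysis unlike that of its own components.
- *Removal is not proven bias.* A reader might infer that dropout inflates the composite above the true rate. That would require the removed subjects to do worse than those retained, and the documents say nothing about this. If missingness were unrelated to outcome, NRI would be the understatement. What can be said is that the rate is higher than the protocol's rule would give.

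**Conclusion.** The point holds as a minor inconsistency. The composite follows a different missing-data rule from the protocol and from both of its components, and the change is not declared. Relative to the protocol rule the reported rate rises by the factor N/(N − m). With N = 60, m from 3 to 12 and every cured subject eradicated, the difference runs from about 2.5 points (28/57 against 28/60) to 10 points (24/48 against 24/60). These sizes rest on assumed mITT size, removals and cure rate.

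It would be too strong to say that the composite will exceed Clinical Cure. It can, and the no-specimen rule makes that plausible, but it depends on how many cured subjects are also eradicated. The primary endpoint is unaffected. The composite is one untested, mITT-only secondary endpoint of an exploratory sub-study, and its outcomes are to be listed, so a reader with the listing could recompute the rate.

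**What to change.** In SAP 13.4.8.2.3, replace the removal rule with one stating that mITT subjects whose overall outcome is undetermined at TOC count as Overall Failures, with the full mITT as denominator. Keep the version without them as a sensitivity summary, as SAP 13.4.8.1.1 does for the primary endpoint, and report how many were removed. If the sponsor prefers removal as the main analysis, declare and justify it in SAP 13.4.11.

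The cost is one SAP sentence and one additional summary. No new data are needed. The reported rate becomes somewhat less favourable, and the composite can no longer exceed its components.

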#### **13.4.8.2.4. Symptom Outcome**

A summary with the number and percentage of subjects with complete resolution of symptoms at the Follow-up (FUP) visit will be performed by Candida Species of the baseline yeast and overall. The subjects with missing Follow-Up data for the symptom outcome will be imputed as symptom persistence using the NRI method described in Section 13.4.4.4.

Symptom outcomes will be assessed at the FU Visit according to the following definitions:

- Symptom Resolution: All symptoms are absent (score = 0) without need for further antifungal treatment or topical vaginal drug therapy for the treatment of vulvovaginal irritation/pruritus prior to or at FU visit;
- Symptom Persistence: No response to therapy or incomplete resolution of symptoms or use of additional vulvovaginal or systemic antifungal therapy or topical vaginal drug therapy for the treatment of vulvovaginal irritation/pruritus prior to or at FU visit. For the subject who early terminated before the FU visit and received additional vulvovaginal or systemic antifungal therapy or topical vaginal drug therapy for the treatment of vulvovaginal irritation/pruritus prior to or at the early termination visit, the subject is considered a symptom persistence.

#### **13.4.8.2.5. Clinical Improvement**

A summary with the number and percentage of subjects with clinical improvement (partial or complete resolution of signs and symptoms with total composite score no greater than 1 without need for further antifungal treatment and topical vaginal drug therapy for the treatment of vulvovaginal irritation/pruritus prior to or at TOC visit) at the TOC visit will be performed. For the subject who early terminated before the TOC visit and received additional vulvovaginal or systemic antifungal therapy or topical vaginal drug therapy for the treatment of vulvovaginal irritation/pruritus prior to or at the early termination visit, the subject is considered no clinical improvement. The subjects with missing TOC visit data for clinical improvement outcome will be imputed as no clinical improvement using the NRI method described in Section 13.4.4.4. The composite score will be calculated as the rules described in Section 13.4.8.1.

#### **13.4.8.2.6. Composite Score of the Vulvovaginal Signs and Symptoms**

The composite score of the vulvovaginal signs and symptoms and Change from Baseline values to test of cure visit and follow up visit will be summarized by treatment and by visit descriptively.

The composite score of the vulvovaginal signs and symptoms will be classified as '0', '1', '2', and '>=3'. This categorical data will be summarized with the frequency and percentage of subjects at each scheduled visit. When there are multiple values within a visit, the worst value will be taken (worst being the maximum value of the composite score of the vulvovaginal signs and symptoms). All analysis will be performed based on the ITT and mITT sets. The similar analyses will be performed for below 2 categorizations of the composite score of the vulvovaginal signs and symptoms: <7, >=7 and '4 - 7', '8 - 12', and '>=13'.

A listing will be provided to present the signs and symptoms score and mycological outcome for all subjects in the ITT set. Assessments that are not done will be presented in the data listing with a missing value.

### 13.4.9. Safety Analysis

Safety analyses will be performed on all subjects in the safety set. Analyses will be based on adverse events, vital signs, clinical laboratory assessments, and physical examination findings. Safety analyses in general will be descriptive and will be presented in tabular format with the appropriate summary statistics.

Individual subject listings will be provided to support the tables.

#### 13.4.9.1. Adverse Events

All AE summaries will be restricted to treatment-emergent AEs (TEAEs) only. A TEAE is defined as any event does not present before exposure to study drug or any event already present that worsens in either intensity or frequency after exposure to study drug.

For the purpose of inclusion in TEAE tables, incomplete AE start and end dates will be imputed as follows:

Incomplete onset dates (where UK and UNK indicate unknown or missing day and month respectively):

- UK-MMM-YYYY: If the month and year are different from the month and year of the date of first dose, assume 01-MMM-YYYY. If the month and year are the same as the month and year for the date of first dose, and the end date (after any imputation) is on or after the date of first dose, then assume the date of first dose. If the month and year are the same as the date of first dose, and the end date (after any imputation) is prior to the date of first dose, then assume the end date for the start date.
- DD-UNK-YYYY/UK-UNK-YYYY: If the year is different from the year of the date of first dose, assume 01-JAN-YYYY of the collected year. If the year is the same as the date of first dose year, and the end date (after any imputation) is on or after the date of first dose, then assume the date of first dose. If the year is the same as the date of first dose, and the end date (after any imputation) is prior to the date of first dose, then assume the end date for the start date.

Incomplete end dates (where UK and UNK indicate unknown or missing day and month respectively):

- UK-MMM-YYYY: Assume the last day of the month;
- DD-UNK-YYYY/UK-UNK-YYYY: Assume 31-DEC-YYYY.

The missing onset dates will be imputed as the date of first dose of study drug. The missing end date will be imputed as the subject's last visit date.

All adverse events will be classified by SOC and PT according to the Medical Dictionary for Regulatory Activities (MedDRA, Version 19.1 or higher).

An overview summary of the number and percentage of subjects with any TEAE, serious TEAE, treatment-related TEAE, treatment-related serious TEAE, TEAE leading to study treatment discontinuation, TEAE leading to study discontinuation, and AE leading to death will be provided by treatment group.

All AEs will be presented in a listing.

#### **13.4.9.1.1. Treatment-Emergent Adverse Events**

Summaries of the total number of TEAEs and the number and percentage of subjects with at least one TEAE will be provided. Treatment-emergent AEs will be presented by SOC and PT. At each level of subject summarization, a subject is counted once if the subject reported one or more events. Percentages will be calculated out of the number of subjects in the safety set.

The summary of TEAEs will be presented in alphabetical order of SOC. Within each SOC, PTs will be sorted in descending order from the PT with the highest total frequency (that is, summed across all treatment groups) to the PT with the lowest total frequency. If the total frequency for any two or more PTs is equal, the PTs will be presented in alphabetical order.

The summarization described above will also be repeated for the following:

- Serious Adverse Events;
- Treatment-Related Adverse Events;
- Treatment-Related Serious Adverse Events;
- Adverse Events Leading to Dose Interruption.

The adverse events with a missing relationship will be considered as “Treatment Related” in the tables.

#### **13.4.9.1.2. Relationship of Adverse Events to Study Treatment**

A summary of TEAEs by relationship to study treatment will be presented in a table. The investigator will provide an assessment of the relationship of the event to the study treatment. The possible relationships are “Not Related” and “Related”. In the TEAE relationship table, if subject reports multiple occurrences of the same TEAE, only the most closely related occurrence will be presented. Treatment-emergent AEs that are missing a relationship will be presented in the summary table as “Related” but will be presented in the data listing with a missing relationship. Percentages will be calculated based on the number of subjects in the safety set.

The TEAE data will be categorized and presented by SOC, PT, and relationship in a manner similar to that described in Section 9.1.1.

Treatment-emergent SAEs by relationship to study treatment will also be presented in a table. Treatment-emergent SAEs that are missing a relationship will be presented in the table as “Related” but will be presented in the data listing with a missing relationship.

#### **13.4.9.1.3. Severity of Adverse Event**

A summary of TEAEs by severity will be presented in a table. The severity that will be presented represents the most extreme severity captured on the CRF page. The possible severities are “Mild”, “Moderate”, and “Severe”.

In the TEAE severity table, if a subject reported multiple occurrences of the same TEAE, only the most severe will be presented. An additional row “Missing” must be added for the missing severity. Percentages will be calculated out of the number of subjects in the safety set.

The TEAE data will be categorized and presented by SOC, PT, and severity in a manner similar to that described in Section 9.1.1.

Additionally, the TEAE data will be categorized and presented by SOC, PT, severity, and relationship. At each combination level of severity and relationship, a subject is counted once if the subject reported one or more events. Percentages will be calculated out of the number of subjects in the safety set.

Treatment-emergent SAEs by severity will also be presented in a table.

#### **13.4.9.1.4. Adverse Events Leading to Treatment Discontinuation**

A summary of the TEAEs with an action taken with study treatment of “Drug Withdrawn” will be presented by treatment in a manner similar to that described in Section 9.1.1.

Any TEAEs leading to treatment discontinuation will be presented in a listing for all subjects.

#### **13.4.9.1.5. Adverse Events Leading to Study Discontinuation**

All subjects who have an AE with the answer to “Caused Study Discontinuation” is “Yes” will be presented in a listing.

#### **13.4.9.1.6. Death**

All subjects who have an AE with an outcome of “Death Related to Adverse Event” will be presented in a listing.

### **13.4.9.2. Clinical Laboratory Evaluations**

Summary tables will be presented for laboratory test results (hematology and blood chemistry) at Screening and TOC visit for subjects in the safety set.

All relevant clinical laboratory tests in chemistry and hematology will be classified as Low, Normal, and High according to the normal ranges. This categorical data will be summarized in shift tables comparing the extreme results at TOC visit with those at the screening visit. Extreme post-baseline results will also be summarized. When there are multiple values within a visit for a particular laboratory variable, the worst value will be taken (worst being the smallest value for criteria below a certain threshold or the largest value for criteria above a certain threshold). If a

subject has a value below the threshold and above the threshold, the value furthest from the threshold will be chosen.

Plots of average clinical laboratory parameters may be presented.

In data listings, laboratory values will be compared to normal ranges; out-of-range laboratory values will be identified.

#### **13.4.9.2.1. Pregnancy**

Female subjects of child-bearing potential will have urine pregnancy tests conducted at screening and at any timepoints during the study, if needed. Only subjects with negative pregnancy test results will be enrolled. Any subjects with positive pregnancy test results at any time during the study will be presented in a listing.

#### **13.4.9.2.2. Events of Clinical Interest**

The frequency and percentage of subjects with the following elevations will be summarized at any post-baseline visit:

- ALT or AST  $> 8 \times$  the upper limit of normal (ULN);
- ALT or AST  $> 5 \times$  ULN for more than 2 weeks or accompanied by total bilirubin  $> 2 \times$  ULN.

A listing will be provided for the above elevations, including the actual measurement of ALT, AST, and total bilirubin, and their reference high limits.

